5.10.2 Secondary Efficacy Parameters

The secondary efficacy parameters include the following:

1. Percent change from baseline to Week 4 in WHSS
2. Change from baseline to Week 8 in WHSS
3. Change from baseline to Week 4 in WHSS

4. Proportion of patients who are overall heartburn responders

An overall heartburn responder is a patient who is a weekly heartburn responder for at least 4 of the 8 treatment weeks and for at least 1 of the final 2 treatment weeks (i.e., Week 7 and Week 8). A weekly heartburn responder is a patient with a decrease of $\geq 30\%$ from baseline in WHSS.

5. Proportion of patients with a DHSS of no more than very mild (≤ 1) on any day during Week 8

6. Proportion of patients with a DHSS of no more than very mild (≤ 1) on any day during Week 4

7. The number of days where DHSS was no more than very mild (≤ 1) during Week 8

8. The number of days where DHSS was no more than very mild (≤ 1) during Week 4

9. Change from baseline in the weekly average of each mRESQ-eD item by week.

10. Proportion of heartburn-free days during Week 8

A heartburn free day is a day where DHSS=0.

11. Proportion of heartburn-free days during Week 4

The continuous parameters (#1, 2, 3, 7, 8, 9, 10, and 11) will be analyzed employing similar methods as described for the primary efficacy parameter.

For the analysis of responder parameters (#4, 5, and 6), the counts and proportion of responders will be calculated for each treatment group. The proportions of responders between each IW-3718 group and the placebo group will be compared using a Cochran-Mantel-Haenszel (CMH) test controlling for esophagitis status. The CMH test is the primary analysis for responder parameters. The difference in the proportion of responders between each IW-3718 group and the placebo group as well as the CMH estimates of odds ratio (IW-3718 over placebo) will be presented, along with the corresponding confidence intervals.

Corresponding to secondary efficacy parameters 7, 8, 10, and 11, additional analyses will be provided for the following parameters: 7a. Proportion of Days where DHSS was no more than very mild (≤ 1) during the 8-week Treatment Period; 8a. Proportion of Days where DHSS was no more than very mild (≤ 1) during the first 4 weeks of the Treatment Period; 10a. Proportion of heartburn-free days during the 8-week Treatment Period; 11a. Proportion of heartburn-free days during the first 4 weeks of the Treatment Period.

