For the analysis of continuous parameters (e.g., absolute change from baseline and percent change from baseline), descriptive statistics (patient number [n], mean, standard deviation, median, and range) will be presented for each treatment group. Each IW-3718 group will be compared with the placebo group using an analysis of covariance (ANCOVA) model with treatment group, and esophagitis stratum as fixed effect terms and the corresponding baseline efficacy parameter value as a covariate. Least-squares means (LSMs) for each treatment group, a linear contrast among the LSMs to test the overall ordinal dose response, LSMs differences between each IW-3718 group and the placebo group and their corresponding confidence intervals, and p-values for the pairwise comparisons versus placebo will be presented. The treatment by esophagitis stratum interaction term will be explored to evaluate whether quantitative or qualitative interaction(s) are present, and treatment comparisons within each stratum will be conducted, as warranted.

The cumulative distribution function (CDF) of change from baseline for key efficacy parameters will be plotted by treatment group. To aid in the interpretation of the graphical representation of the CDF across treatments, a two-sample Kolmogorov-Smirnov test will be conducted (22). A

p-value ≤ 0.05 indicates that the 2 treatment samples are unlikely to have been drawn from the same continuous distribution by chance alone.

For the analysis of responder parameters (i.e., responder vs. non-responder), the counts and proportion of responders will be calculated for each treatment group. The proportions of responders between each IW-3718 group and the placebo group will be compared using a Cochran-Mantel-Haenszel (CMH) test controlling for esophagitis stratum. The CMH test is the primary analysis for responder parameters. The difference in the proportion of responders between each IW-3718 group and the placebo group as well as the CMH estimates of the odds ratio (IW-3718 over placebo) and the corresponding 95% confidence intervals will also be presented.

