2. STUDY OBJECTIVES

The objectives of this study are to evaluate the safety, efficacy, and dose-response relationship of IW-3718 administered orally to patients who have gastroesophageal reflux disease (GERD) and continue to experience GERD symptoms while receiving once-daily (QD), optimized, standard-dose proton pump inhibitors (PPIs).

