5.1.3 Statistical Significance and Multiplicity

All hypothesis tests will be two-sided with a 5% significance level, and 95% confidence intervals will be used, unless stated otherwise. No adjustments for multiplicity are planned; p-values will be reported as nominal.

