5.10.3 Other Efficacy Parameters

Other efficacy parameters include the following:

1. Percent change from baseline to Week 8 in weekly regurgitation frequency score (WRFS) in patients with a baseline WRFS of ≥ 2 (sometimes)

The WRFS for an analysis week is defined as the average of available daily regurgitation frequency scores (DRFS) during that week. DRFS is defined as the maximum of the 2 items measuring regurgitation (Regurgitation [liquid or food moving upwards toward your throat or mouth] and An acid or bitter taste in the mouth) from a particular day collected with the mRESQ-eD instrument.

2. Percent change from baseline to Week 4 in WRFS in patients with a baseline WRFS of 2 (sometimes)

3. Change from baseline to Week 8 in WRFS

4. Change from baseline to Week 4 in WRFS

5. Proportion of patients who are overall regurgitation responders (of patients with a baseline WRFS of ≥ 2 [sometimes])

An overall regurgitation responder is a patient who is a weekly regurgitation responder for at least 4 of the 8 treatment weeks and for at least 1 of the final 2 treatment weeks (i.e., Week 7 and Week 8). A weekly regurgitation responder is a patient with a decrease of $\geq 30\%$ from baseline in WRFS.

6. Proportion of patients with a DRFS of no more than rarely (≤ 1) on any day during Week 8

7. Proportion of patients with a DRFS of no more than rarely (≤ 1) on any day during Week 4

8. Change from baseline to Week 8 in the number of days per week where DRFS was no more than rarely (≤ 1)

9. Change from baseline to Week 4 in the number of days per week where DRFS was no more than rarely (≤ 1)

10. Change from baseline to Week 8 in the weekly average of each of the daily symptom assessments

11. Weekly means for daily sleep assessments (number of awakenings, hours of sleep, sleep quality)

12. Weekly means for weekly symptom bothersomeness assessments, symptom relief assessments, and treatment satisfaction assessment

For analysis of continuous parameters (#1, 2, 3, 4, 8, 9, 10, 11, and 12), summary statistics will be presented by treatment group. Each IW-3718 group will be compared with the placebo group using an ANCOVA model with treatment group and esophagitis status as fixed-effect terms and

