the corresponding baseline efficacy parameter value as a covariate. Note that for parameters without a baseline value (e.g., Treatment Satisfaction), an ANOVA model (in lieu of ANCOVA) will be used with treatment group and esophagitis status as fixed-effect terms.

For analysis of responder parameters (#5, 6, and 7), the counts and proportion of responders will be calculated for each treatment group. The proportions of responders between each IW-3718 group and the placebo group will be compared using a CMH test controlling for esophagitis status.

Corresponding to efficacy parameters 8 and 9, additional analyses will be provided for the following parameters: 8a. Change from baseline to the 8-week Treatment Period in proportion of days where DRFS was no more than rarely (≤ 1); 9a. Change from baseline to the first 4 weeks of Treatment Period in proportion of days where DRFS was no more than rarely (≤ 1).

Change/percent change from baseline in WHSS, WRFS, and the weekly average of each of the individual daily symptom assessment items (GERD & dyspepsia) will be summarized/analyzed by week, and the LS mean changes/LS mean percent changes will be plotted across treatment weeks.

The proportion of Degree of Relief responders (reported a score of 1-Significantly Relieved or 2-Moderately Relieved on the Degree of Relief question for at least 4 of the 8 treatment weeks) will be summarized by treatment group for heartburn, regurgitation, and overall GERD symptoms.

In addition, the GSRS-self will be summarized by treatment group by visit for each of the 15 items and for each of the 5 domains: abdominal pain (3 items), reflux symptoms (2 items), indigestion (4 items), diarrhea (3 items), and constipation (3 items). The EOT Visit difficulty of swallowing question will also be summarized by presenting the count and proportion of patients in each of the 4 categories (from Not at all Difficult to Extremely Difficult) by treatment group.

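### Dose response is a study objective, but the SAP names no test across all four arms for the heartburn responder secondaries or the WRFS/DRFS parameters

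*SAP*

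**What the plan says.** SAP section 2 gives the aim: "The objectives of this study are to evaluate the safety, efficacy, and dose-response relationship of IW-3718". SAP 5.13 and Protocol 3.7.7 size the trial on a linear trend test over placebo and the three doses, with a pairwise comparison following it.

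Protocol 3.7.4.1 provides, for continuous primary and secondary parameters, "a linear contrast among the LSMs to test the overall ordinal dose response". SAP 5.10.1 repeats this for the primary parameter. SAP 5.10.2 extends it to continuous secondaries #1-3 and #7-11 by saying that they are analysed with methods similar to the primary.

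For responder secondaries #4-6, SAP 5.10.2 specifies a CMH test of each dose against placebo, controlling for esophagitis status, and adds "The CMH test is the primary analysis for responder parameters". Differences and odds ratios by dose, with confidence intervals, are also reported.

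For the continuous parameters in SAP 5.10.3, which include WRFS/DRFS #1-4, 8 and 9: "Each IW-3718 group will be compared with the placebo group using an ANCOVA model with treatment group and esophagitis status as fixed-effect terms". For #5-7: "The proportions of responders between each IW-3718 group and the placebo group will be compared using a CMH test controlling for esophagitis" status. No contrast or trend statistic is mentioned. Protocol 3.7.4.2 gives the continuous parameters the same pairwise ANCOVA and describes no further test.

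On error control, SAP 5.1.3 states "All hypothesis tests will be two-sided with a 5% significance level" and "No adjustments for multiplicity are planned; p-values will be reported as nominal". Protocol 3.7.2 gives the exploratory nature of the trial as the reason.

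**The concern.** Three comparisons that share one placebo arm each ask whether a given dose differs from placebo. None asks whether response rises with dose. For the parameters above, no specified analysis uses all four arms, and the CMH wording cannot be read as covering a trend statistic because each comparison is one dose against placebo.

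This matters most for the overall heartburn responder (#4), the patient-level counterpart of the primary parameter. As planned, the trial can test whether mean WHSS change is ordered by dose, but it has no planned test of whether the response rate is. Protocol 3.5.2 also counts regurgitation symptoms among the assessments behind the key efficacy parameters. If a trend test on these parameters is wanted after unblinding, its statistic, dose scores and stratification would be chosen with the results in view. SAP section 6 lists two changes from the protocol, both about analysis populations, so the gap is not dealt with there.

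**Working it through.** **1. The plan's own power figures (SAP 5.13).** Inputs: difference 0.70, SD 1.35, 58 per arm, two-sided 5%, arm effects 0 / 55% / 55% / 110% of 0.70, that is 0, 0.385, 0.385, 0.77.
- Trend, contrast (-3, -1, 1, 3): value = -0.385 + 0.385 + 3 × 0.77 = 2.31. Standard error = 1.35 × √(20/58) = 0.793. Ratio = 2.91. Power = Φ(2.91 − 1.96) = 83.0% (82.7% with the t distribution, 228 df).
- Pairwise: 0.70 / (1.35 × √(2/58)) = 2.79. Power = Φ(2.79 − 1.96) = 79.7%.

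Both agree with the stated figures of at least 80% and 80%. The documents give no power for the responder or regurgitation parameters.

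**2. Coverage, parameter by parameter.**

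| Parameters | Pairwise tests | Test across four arms |
|---|---|---|
| Primary; 5.10.2 #1-3, 7-11 | ANCOVA | Linear contrast |
| 5.10.2 #4-6 | CMH | None |
| 5.10.3 #1-4, 8, 9 | ANCOVA | None |
| 5.10.3 #5-7 | CMH | None |

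Secondary #9 is the change in each mRESQ-eD item. SAP 4.1.1.1 lists regurgitation and the acid or bitter taste among those items, so both components of DRFS already get the contrast.

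**3. What the three pairwise tests do under no effect.** With equal allocation, any two dose-versus-placebo statistics correlate 0.5. The chance of at least one |z| > 1.96 is

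1 − ∫ φ(x) [Φ(x + 1.96√2) − Φ(x − 1.96√2)]³ dx = 12.5%.

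The chance that at least one dose is significantly better than placebo is 6.3%. Simulated stratified CMH tests (65 per arm, assumed responder rates 10-50%, assumed erosive share 30% or 50%) give 11.1-12.7% and 5.6-6.2%. Adding a trend test with no gating raises the two-sided chance of any significant result from 12.5% to 13.5%. Reading the pairwise tests only after a significant trend would bring the chance of declaring any dose to 4.0%.

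**4. What a trend test would add.** In stratum h, let x be the responders in arm k, n its size, m the total responders and N the total patients, with scores s = 0, 1, 2, 3. The statistic is T²/V on 1 df, with T = Σ_h Σ_k s_k (x_hk − n_hk m_h/N_h) and V = Σ_h [m_h(N_h − m_h) / (N_h(N_h − 1))] × Σ_k n_hk (s_k − s̄_h)². Simulation used 65 per arm, 200,000 trials per case and an erosive share of 20-60%. The responder rates and erosive shares are assumptions, because the documents give neither.

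| Rates: placebo / low / middle / high | Trend test | Pairwise test |
|---|---|---|
| Equal, 20-50% | 4.9-5.1% | about 4-5% each |
| 30 / 36.7 / 43.3 / 50% | 69-70% | 65% (high dose) |
| 30 / 35 / 40 / 45% | 46% | 43% (high dose) |
| 30 / 40 / 40 / 50% (planning shape) | 60% | 65% (high dose) |
| 30 / 45 / 45 / 45% (plateau) | 38% | 43% (each dose) |
| 30 / 50 / 30 / 30% (low-dose peak) | 11% | 65% (low dose) |

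**The case against.** The strongest case against is that this is an exploratory Phase 2b trial, and a dose-response objective does not oblige a trend test on every endpoint. The contrast covers the primary parameter and eight continuous secondaries, including days with no more than very mild heartburn and heartburn-free days. Responder #4 dichotomises the same WHSS. Readers will also see the response rate in every arm, with differences and odds ratios, so an ordering by dose will be visible even without a test. And the trend test is not uniformly stronger: on the sponsor's planning shape and on a plateau it has less power than a single pairwise test.

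Most of that stands. It means the gap is one of pre-specification and not an error in the primary analysis, and it argues against ranking the trend test above the pairwise tests. It does not remove the gap, since a visible ordering is not a planned test of it.

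Three stronger inferences might tempt a reader, and the documents do not support them:
- That every regurgitation endpoint lacks a trend test. The two item scores are covered through secondary #9.
- That the missing trend test causes the 12% chance of a nominally significant dose. That figure comes from three unadjusted tests. The primary parameter has it too, because its contrast is not stated as a gate.
- That 12% is the chance of wrongly finding a beneficial dose. It counts both directions; the beneficial direction is about 6%. The absence of adjustment is disclosed and p-values are labelled nominal.

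**Conclusion.** The gap is real and limited. For 5.10.2 #4-6 and 5.10.3 #1-9 the SAP specifies no test across the four arms, although dose response is an objective and the trial was sized on a trend. A pre-specified test would give each of these parameters one dose-response answer at the 5% level. It would not lower the 12% two-sided (6% beneficial) chance from the pairwise tests.

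The coverage finding rests on the text alone. The power figures rest on assumed responder rates, an assumed erosive share and 65 patients per arm. The planning shape in SAP 5.13 concerns mean NRS change, so applying it to response rates is itself an assumption. Regurgitation parameters #1, 2 and 5 are restricted by baseline WRFS, so their numbers are smaller and unknown, and these powers do not carry over to them.

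**What to change.** Before unblinding:
- In SAP 5.10.2 for #4-6 and in 5.10.3 for #5-7, add a 1-df CMH correlation (trend) test over all four arms, stratified by esophagitis status, with equally spaced dose scores 0, 1, 2, 3.
- In SAP 5.10.3 for #1-4, 8 and 9, add the linear contrast among LS means already used in 5.10.1.
- Describe each as the pre-specified dose-response test, presented alongside the existing pairwise tests and estimates, with all p-values nominal as now planned and no gating implied.
- Align Protocol 3.7.4.1 and 3.7.4.2.

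The cost is a few sentences and one more statistic per table, with no new data or patients. The downside is one more nominal p-value per parameter, from a test that loses power on a plateau (38% in the example) and is weak if response peaks at a low dose (11%). That is why the pairwise estimates stay in the tables.

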5.10.3 Other Efficacy Parameters

Other efficacy parameters include the following:

1. Percent change from baseline to Week 8 in weekly regurgitation frequency score (WRFS) in patients with a baseline WRFS of ≥ 2 (sometimes)

The WRFS for an analysis week is defined as the average of available daily regurgitation frequency scores (DRFS) during that week. DRFS is defined as the maximum of the 2 items measuring regurgitation (Regurgitation [liquid or food moving upwards toward your throat or mouth] and An acid or bitter taste in the mouth) from a particular day collected with the mRESQ-eD instrument.

2. Percent change from baseline to Week 4 in WRFS in patients with a baseline WRFS of 2 (sometimes)

3. Change from baseline to Week 8 in WRFS

4. Change from baseline to Week 4 in WRFS

5. Proportion of patients who are overall regurgitation responders (of patients with a baseline WRFS of ≥ 2 [sometimes])

An overall regurgitation responder is a patient who is a weekly regurgitation responder for at least 4 of the 8 treatment weeks and for at least 1 of the final 2 treatment weeks (i.e., Week 7 and Week 8). A weekly regurgitation responder is a patient with a decrease of $\geq 30\%$ from baseline in WRFS.

6. Proportion of patients with a DRFS of no more than rarely (≤ 1) on any day during Week 8

7. Proportion of patients with a DRFS of no more than rarely (≤ 1) on any day during Week 4

8. Change from baseline to Week 8 in the number of days per week where DRFS was no more than rarely (≤ 1)

9. Change from baseline to Week 4 in the number of days per week where DRFS was no more than rarely (≤ 1)

10. Change from baseline to Week 8 in the weekly average of each of the daily symptom assessments

11. Weekly means for daily sleep assessments (number of awakenings, hours of sleep, sleep quality)

12. Weekly means for weekly symptom bothersomeness assessments, symptom relief assessments, and treatment satisfaction assessment

For analysis of continuous parameters (#1, 2, 3, 4, 8, 9, 10, 11, and 12), summary statistics will be presented by treatment group. Each IW-3718 group will be compared with the placebo group using an ANCOVA model with treatment group and esophagitis status as fixed-effect terms and

the corresponding baseline efficacy parameter value as a covariate. Note that for parameters without a baseline value (e.g., Treatment Satisfaction), an ANOVA model (in lieu of ANCOVA) will be used with treatment group and esophagitis status as fixed-effect terms.

For analysis of responder parameters (#5, 6, and 7), the counts and proportion of responders will be calculated for each treatment group. The proportions of responders between each IW-3718 group and the placebo group will be compared using a CMH test controlling for esophagitis status.

Corresponding to efficacy parameters 8 and 9, additional analyses will be provided for the following parameters: 8a. Change from baseline to the 8-week Treatment Period in proportion of days where DRFS was no more than rarely (≤ 1); 9a. Change from baseline to the first 4 weeks of Treatment Period in proportion of days where DRFS was no more than rarely (≤ 1).

Change/percent change from baseline in WHSS, WRFS, and the weekly average of each of the individual daily symptom assessment items (GERD & dyspepsia) will be summarized/analyzed by week, and the LS mean changes/LS mean percent changes will be plotted across treatment weeks.

The proportion of Degree of Relief responders (reported a score of 1-Significantly Relieved or 2-Moderately Relieved on the Degree of Relief question for at least 4 of the 8 treatment weeks) will be summarized by treatment group for heartburn, regurgitation, and overall GERD symptoms.

In addition, the GSRS-self will be summarized by treatment group by visit for each of the 15 items and for each of the 5 domains: abdominal pain (3 items), reflux symptoms (2 items), indigestion (4 items), diarrhea (3 items), and constipation (3 items). The EOT Visit difficulty of swallowing question will also be summarized by presenting the count and proportion of patients in each of the 4 categories (from Not at all Difficult to Extremely Difficult) by treatment group.

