3.7.4.2 Other Efficacy Parameters

Other efficacy parameters include the following:

1. Percent change from baseline in weekly regurgitation frequency scores (WRFS) to (a) Week 4 and (b) Week 8 in patients with a mean baseline regurgitation frequency of ≥ 2 (sometimes).
2. Change from baseline in WRFS to (a) Week 4 and (b) Week 8
3. Proportion of patients who are overall regurgitation responders (of patients with a baseline regurgitation frequency of ≥ 2 [sometimes])
 - a. Weekly regurgitation responder: patient with a decrease from baseline of $\geq 30\%$ in WRFS
 - b. Overall regurgitation responder: patient who is a weekly responder for at least 1 of the final 2 weeks and for $\geq 50\%$ of the treatment weeks
4. Proportion of patients with regurgitation frequency of no more than rarely (daily regurgitation frequency score [DRFS] ≤ 1) on any day during (a) Week 4 and (b) Week 8
5. Change from baseline to (a) Week 4 and (b) Week 8 in the number of days per week where DRFS was no more than rarely (≤ 1)
6. Change from baseline to Week 8 in weekly means for each of the daily symptom assessments

Note: DRFS is the maximum of the 2 items in the regurgitation domain scores of a particular day, collected with the mRESQ-eD instrument. Similarly, WRFS is defined as the average of DRFS in a particular week. A DRFS of zero is considered Regurgitation Free for a particular day.

7. Weekly means for daily sleep assessments (number of awakenings, hours of sleep, sleep quality)
8. Weekly means for weekly symptom bothersomeness assessments, symptom relief assessments, and treatment satisfaction assessment
9. Exploratory non-efficacy parameters and analysis:
 - a. Summarize patient baseline disease characteristics and key efficacy differences for patients with or without Bilitec monitoring performed during the Screening Period
 - b. Compare patient baseline disease characteristics and key efficacy parameters between bile acid positive versus bile acid negative patients (on the subgroup of patients with Bilitec monitoring during the Screening Period).
 - c. Assess sensitivity and specificity (i.e., receiver operating characteristic [ROC] curve) of bile acid levels measured in saliva as a test for bile acid pathophysiology with Bilitec test findings as the reference standard (on the subgroup of patients with Bilitec monitoring during the Screening Period)
 - d. Utilize bile acid levels in saliva as a predictor of response to treatment

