5.10 EFFICACY ANALYSIS

Unless otherwise specified, efficacy analyses will be based on both the mITT and the PP Populations.

Baseline values for efficacy parameters will be derived from the eDiary and/or electronic clinical report form (eCRF) data collected for the last week of the Pretreatment Period (or Week -1), specifically the period from 7 days prior to the day of randomization up to the time of randomization. If data for Week -1 is not available, data for Week -2 (the second last week of the Pretreatment Period) will be used.

For continuous efficacy parameters, the analysis value for an analysis period is defined as the average of the non-missing values during that period.

For weekly responder parameters based on daily eDiary assessments, a patient who missed 4 or more daily assessments during an analysis week will not be considered a responder for that week.

[Table 5.10-1](#) provides the analysis time windows allowed for efficacy analyses based on daily assessments and [Table 5.10-2](#) provides the analysis time windows allowed for efficacy analyses based on weekly assessments.

Table 5.10-1. Analysis Time Windows for Efficacy Analysis – Daily Assessments

Period	Analysis Week	Begins ^a	Ends ^a
Pretreatment (Baseline ^b)	Week -2	Day -14	Day -8
	Week -1	Day -7	Day -1 (Day before randomization) ^c
Treatment	Week 1	Day 1 (Day of Randomization) ^d	Day 7
	Week 2	Day 8	Day 14
	Week 3	Day 15	Day 21
	Week 4	Day 22	Day 28
	Week 5	Day 29	Day 35
	Week 6	Day 36	Day 42
	Week 7	Day 43	Day 49
	Week 8	Day 50	Day 56
	Week 9	Day 57	Day 63
	***	***	***

- a. Relative to the date of randomization (Day 1).
- b. Baseline values for efficacy parameters will be derived from the daily eDiary collected in the Pretreatment Period Week -1 (Week -2 if data from Week -1 not available)
- c. Day 1 for efficacy parameters derived from the morning diary.
- d. Day 2 for efficacy parameters derived from the morning diary.

Table 5.10-2. Analysis Time Windows for Efficacy Analysis – Weekly Assessments

Period	Analysis Week	Begins ^a	Ends ^a
Pretreatment (Baseline ^b)	Week -2	Day -11	Day -5
	Week -1	Day -4	Day -1 (Day before randomization)
Treatment	Week 1	Day 7	Day 10
	Week 2	Day 11	Day 17
	Week 3	Day 18	Day 24
	Week 4	Day 25	Day 31
	Week 5	Day 32	Day 38
	Week 6	Day 39	Day 45
	Week 7	Day 46	Day 52
	Week 8	Day 53	Day 59
	Week 9	Day 60	Day 66

a. Relative to the date of randomization (Day 1).

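### SAP 5.10.3 #2 sets the Week 4 regurgitation percent-change subset at a baseline WRFS of 2, where SAP #1, SAP #5 and the protocol say at least 2: most likely a dropped ≥ sign

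*SAP*

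**What the plan says.** Protocol 3.7.4.2 #1 defines one subset for percent change in WRFS at both time points: "to (a) Week 4 and (b) Week 8 in patients with a mean baseline regurgitation frequency of ≥ 2 (sometimes").

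SAP 5.10.3 splits this into two parameters. For Week 8 (#1) the analysis is "in patients with a baseline WRFS of ≥ 2 (sometimes"). For Week 4 (#2) it is "Percent change from baseline to Week 4 in WRFS in patients with a baseline WRFS of 2 (sometimes"), without the inequality sign. The responder parameter (#5) has the sign again: "Proportion of patients who are overall regurgitation responders (of patients with a baseline WRFS of ≥ 2 [sometimes").

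The SAP makes WRFS a mean, not a single rating: "The WRFS for an analysis week is defined as the average of available daily regurgitation frequency scores (DRFS) during that week". SAP 5.10 takes the baseline from "data collected for the last week of the Pretreatment Period (or Week -1"), falling back on Week -2 if that week has no data. Parameter #2 is among those analyzed by ANCOVA with treatment group, esophagitis status and "the corresponding baseline efficacy parameter value as a covariate".

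SAP Section 6 lists two changes from the protocol. Both concern the Randomized Population and neither concerns this subset.

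**The concern.** The subset rule decides who enters the analysis, so a programmer has to implement it one way or the other. As worded, #2 differs from its Week 8 twin, from the responder parameter in the same list and from the protocol, and nothing in the SAP explains the difference.

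Applied literally, the rule has four consequences:

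- Only patients whose mean over the baseline week is exactly 2.00 qualify.
- Everyone above 2 is excluded, and these are the patients with more frequent regurgitation. The SAP allows for such patients, because 5.10.5 plans a Week 8 percent-change subgroup at baseline WRFS above 3.
- The ANCOVA covariate takes one value, so its slope cannot be estimated.
- The Week 4 and Week 8 results describe different patients and cannot be read as a time course.

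**Working it through.** **The plan's own figure.** The only power figures in the documents concern heartburn. With a difference of 0.70, SD 1.35, 58 per arm and two-sided α 0.05:

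- Pairwise power = Φ(0.70 / (1.35 × √(2/58)) − 1.96) = Φ(2.79 − 1.96) = 79.7%, against 80% stated.
- Trend power, with contrast (−3, −1, 1, 3) on effects 0, 0.385, 0.385, 0.77 = Φ(2.31 / (1.35 × √(20/58)) − 1.96) = Φ(2.91 − 1.96) = 83.0%, against at least 80% stated.

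Both reproduce. Neither depends on the regurgitation subset, so this point leaves the sample size alone.

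**The wordings side by side.**

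| Place | Time point | Baseline rule |
|---|---|---|
| Protocol 3.7.4.2 #1 | Weeks 4 and 8 | ≥ 2 |
| SAP 5.10.3 #1 | Week 8 | ≥ 2 |
| SAP 5.10.3 #2 | Week 4 | 2 |
| SAP 5.10.3 #5 | Overall responder | ≥ 2 |
| SAP Section 6 | – | no change listed |

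**How narrow exactly 2 is.** The daily score is the larger of two 0-to-4 items, so it is an integer from 0 to 4. With d diary days the weekly mean has 4d + 1 possible values: 29 with seven days, and 21 with the five days that eligibility requires as a minimum. Exactly 2.00 is one of them.

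**What happens to the model.** If every baseline equals 2, the covariate is a multiple of the intercept. The model then reduces to treatment group and esophagitis status. Treatment differences could still be estimated, but without the planned adjustment. Percent change becomes 100 × change / 2 = 50 × change, which is the absolute change rescaled. None of this depends on the baseline distribution.

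**How many patients: assumptions only.** Neither document gives a baseline WRFS distribution, an entry threshold for regurgitation or an expected subset size. One approach takes a normal distribution for the baseline mean, truncated to 0–4 and cut into bins of width 1/d. With h = 1/(2d):

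P(exactly 2) = [Φ((2 + h − μ)/σ) − Φ((2 − h − μ)/σ)] / [Φ((4 − μ)/σ) − Φ((0 − μ)/σ)]

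For μ = 2.0, σ = 1.0, d = 7 this is 0.0569 / 0.9545 = 0.060, or 3.5 of the 58 per arm expected at Week 8 and 3.9 of the 65 randomized. A second approach simulates seven integer daily scores around each patient's own mean, with an assumed day-to-day SD of 0.3 to 0.9.

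| Assumed baseline WRFS | Exactly 2.00, of 58 | At least 2, of 58 |
|---|---|---|
| mean 1.5, SD 0.6, 7 days | 3.9 | 13.9 |
| mean 1.5, SD 0.6, daily SD 0.3 | 6.6 | 15.6 |
| mean 2.0, SD 1.0, 7 days | 3.5 | 30.7 |
| mean 2.0, SD 0.6, daily SD 0.3 | 9.2 | 33.7 |
| mean 2.5, SD 0.8, 7 days | 3.5 | 43.8 |
| mean 3.0, SD 0.6, 7 days | 1.4 | 55.7 |
| all 29 values equally likely | 2.0 | 30.0 (58 × 15/29) |

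Across means of 1.5 to 3.0 and between-patient SDs of 0.6 to 1.2, exactly 2.00 gives about 1.4 to 9.2 of 58 (1.6 to 10.3 of 65). At least 2 gives about 14 to 56 of 58. The literal subset is smaller under every assumption tried: from 1.4 / 55.7 = 3% of the intended one up to 6.6 / 15.6 = 42%.

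**What that means for precision.** The standardized difference detectable with 80% power is (1.96 + 0.84) × √(2/n): 1.25 SD at n = 10 per arm, against 0.72 SD at n = 30. The normal approximation flatters the smaller number.

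**The case against.** The strongest reply is that nobody would apply the literal rule. The same list uses ≥ 2 twice, the SAP presents itself as an elaboration of the protocol, a fixed baseline makes the chosen covariate pointless, and the silence of Section 6 suggests that no change was meant. The symbol may even be present in the source file and lost in conversion of the PDF to text. This largely stands on the question of intent. A reader might infer a deliberate, undeclared narrowing of the Week 4 population, and the documents do not support that. Conversion loss is possible, but the ≥ sign survives in #1, in #5 and in the 30% responder rule of the same section, and ≤ survives in #6 to #9. The available wording therefore has to be treated as a conflict until the source is checked.

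A reader might also infer a definite count, such as three or four patients per arm. Some assumptions give that and others do not, and the documents cannot choose between them.

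Finally, a reader might infer that Week 4 regurgitation evidence would be lost. It would not. SAP 5.10.3 #4 gives absolute Week 4 change in WRFS with no baseline threshold, #7 and #9 give further Week 4 results, and the same section has percent change in WRFS analyzed by week. That by-week analysis does not replace #2, however, because no baseline subset is stated for it. Protocol 3.3.1.1 sets a diary threshold for heartburn only (criterion 6), and criterion 3 accepts heartburn or regurgitation. Baseline WRFS can therefore be near zero, where percent change is unstable, or zero, where it is undefined. The parameter that the protocol names would still not be correctly specified for Week 4.

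**Conclusion.** The conflict holds and the wording of #2 needs correcting. It is most likely typographical. If applied as written, it would select the wrong patients for one table, empty the covariate adjustment of meaning and break the match between Week 4 and Week 8. Those consequences follow from the definitions alone. The size of the literal subset does not: roughly 1 to 10 per arm is a range over assumed baseline distributions and should be quoted only as such.

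The importance is minor. Parameter #2 is in the other-efficacy tier, p-values are nominal with no multiplicity adjustment (SAP 5.1.3), and the primary parameter, the secondary parameters and the sample size are unaffected.

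**What to change.** Check the SAP source file. If the sign is missing there, change the subset in 5.10.3 #2 to a baseline WRFS of ≥ 2 (sometimes), matching #1, #5 and protocol 3.7.4.2 #1, and confirm that the table specifications and programs for #1 and #2 use the same subset flag. The cost is one symbol and a short programming check, with no new data or design decision and no entry needed in SAP Section 6, since the correction restores the protocol's rule. If the restriction to exactly 2 was in fact intended, Section 6 should declare it with a reason, and the covariate should be removed from the model for #2.
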